10.1 Definitions

For definition of “target lesion”, “progressive disease” (PD), “partial response” (PR) and “complete response” (CR) please refer to section 10.2.1.

10.1.1 CTC clearance rate

The CTC clearance rate is defined as the proportion of patients with at least one CTC detected in 7.5 ml of peripheral blood drawn before treatment that show no evidence of CTCs in the blood after treatment (CTC prevalence as assessed using the Cell-Search® System; Veridex LLC, Raritan, USA).

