2.3 Circulating tumor cells

Hematogenous tumor cell dissemination is a crucial step in tumor progression, and blood-derived metastases account for the majority of breast cancer-related deaths. Cells that are able to disseminate into the circulation are of biologic relevance as potential founder cells for new metastases, and CTC detection and characterization have already improved our understanding of the complex process underlying tumor cell dissemination and metastatic progression in breast cancer.

Previous research has shown that CTCs ($\geq 1 / 7.5$ ml blood) are present in 65-85% of patients with MBC (Fehm et al. 2010, Botteri et al. 2010, Müller et al. 2012, Pierga et al. 2012), and five or more CTCs are detected in about 40-50% of MBC patients (Cristofanilli et al. 2004, Budd et al. 2006, Fehm et al. 2010, Müller et al. 2012, Pierga et al. 2012). There is good evidence that CTCs detected in the peripheral blood of patients with MBC can both provide prognostic information (Budd et al. 2006, Cristofanilli et al. 2005, Hayes et al. 2006, Giuliano et al. 2011, Giordano et al. 2012, Wallwiener et al. 2013) and indicate therapy success (Liu et al. 2009, Pierga et al. 2012).

The FDA approved standardized and semi-automatic CellSearch™ system (Veridex, LLC, USA) will be used for capture, isolation and enumeration of CTCs. The method has been described in detail in a validation study by Riethdorf et al. 2007, and is now routinely being used in the laboratories responsible for conducting the translational research program in the DETECT IV study. Briefly, blood samples are collected into special CellSave tubes, centrifuged to separate solid blood components from plasma, and then placed in the CellTracks® AutoPrep® System. Using ferrofluid nanoparticles with antibodies that target epithelial cell adhesion molecule (anti-EpCAM), CTCs are magnetically separated from the other cells in the blood. CTCs are then stained with the fluorescent nucleic acid dye 4',6-diamidino-2-phenylindole (DAPI), cytokeratin monoclonal antibodies (specific to epithelial cells) and a

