2.10 Translational Medical Investigations

2.10.1 In General

Translational medical investigations will be performed in patients who consent in blood sampling for this purpose (patient information and consent form - part 3). At predefined time points during study participation, peripheral blood will be drawn from the patients and collected in tubes provided by the sponsor:

Provided Kit	Blood volume
Screening Kit	Approx. 40 ml (10 ml for CTC detection, 30 ml for additional research)
Analysis Kit	Approx. 50 ml (10 ml for CTC detection, 40 ml for additional research)

Table 3: Bloodkits for translational research

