5.1 Eligibility Criteria

In General for both study cohorts															

 1. Metastatic breast cancer, which cannot be cured by surgery or radiotherapy. The primary tumor and/or biopsies must have been confirmed as cancer by histopathology. 2. HER2 status (as investigated on all primary tumor tissue and/or biopsies from metastatic sites or loco regional recurrences) must be negative. HER2-negativity is defined as (i.e.: immunohistochemistry (IHC) score 0-1+ or 2+ and fluorescent in situ hybridization (FISH) negative or just FISH negative, whichever was performed) in all tissue samples. 3. Evidence of CTCs. At least one CTC has been detected in 7.5 ml patient blood by means of the CellSearch® Circulating Tumor Cell Kit (Veridex LLC, Raritan, USA). 4. HER2 negativity of all detected CTCs. 5. Adequate organ function within 7 days before date of recruitment, evidenced by the following laboratory results: 
 
 - absolute neutrophil count	$\geq 1500/\mu\text{L}$,	
 
 - platelet count	$\geq 100000/\mu\text{L}$,	
 
 - hemoglobin	$\geq 9 \text{ g/dL}$,	
 
 - ALT (SGPT)	$\leq 3.0 \times \text{ULN}$,	
 
 - AST (SGOT)	$\leq 3.0 \times \text{ULN}$,	
 
 - Bilirubin	$\leq 2.0 \times \text{ULN}$	
 
 - creatinine	$\leq 2.0 \times \text{ULN}$.	
 
 6. Written informed consent in study participation. 7. Undergoing a re-biopsy prior to inclusion if tissue is accessible, which can be safely biopsied, is optional but desirable. 8. Tumor evaluation has been performed within 6 weeks before date of recruitment and results are available. 9. Patients must have at least one not previously irradiated lesion that can be evaluated according to RECIST version 1.1 (Eisenhauer 2009). Patients with measurable and non-measurable disease are eligible. Presence of clinically and/or radiologically documented disease. 10. Age ≥ 18 years. 11. ECOG Performance Status ≤ 2. 		- absolute neutrophil count	$\geq 1500/\mu\text{L}$,	- platelet count	$\geq 100000/\mu\text{L}$,	- hemoglobin	$\geq 9 \text{ g/dL}$,	- ALT (SGPT)	$\leq 3.0 \times \text{ULN}$,	- AST (SGOT)	$\leq 3.0 \times \text{ULN}$,	- Bilirubin	$\leq 2.0 \times \text{ULN}$	- creatinine	$\leq 2.0 \times \text{ULN}$.
- absolute neutrophil count	$\geq 1500/\mu\text{L}$,														

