6.3 Actions taken on Inclusion/Recruitment Visit

- **Note on Time schedule:** Examinations and data collections for the so-called Inclusion/ Recruitment Visit are not necessarily to be performed on one single day, but can be done on several days over the following period of time: **From obtaining informed consent - part 2 to day 21 after Screening Visit at the latest.** Please

observe also the time intervals allowed for the results of several examinations (see TABLE 12 below). Results obtained before Inclusion/ Recruitment Visit may be employed if they meet the given time interval. However, the given flexibility during the Inclusion/ Recruitment Visit requires exact documentation of time and date of every result.

- If HER2 status on CTC is negative, informed consent in study participation is obtained (see section 17.4 and patient information and consent form – part 2). Before this no study procedure must be carried out except procedures planned on the Screening Visit.
- In addition, informed consent in blood sampling for translational investigations is obtained (see section 17.4 and patient information and consent form – part 3). If a patient objects to blood sampling for this purpose, she may nevertheless participate in the study.
- Medical/surgical history, concomitant diseases and ongoing toxicities attributed to prior anticancer therapies (denomination, date of onset, end date / specification if ongoing; in case of toxicities additionally: severity according to NCI CTCAE 4.03, treatment the toxicity is attributed to).
- Prior anti-cancer medication, other relevant prior medication (e.g. treatment of toxicities), concomitant medication (denomination, start date, dosage, route, end date/specification if ongoing, indication).
- Physical examination.
- Vital signs (heart rate, blood pressure, body temperature), height and weight.
- Blood sampling for hematology and biochemistry (see also TABLE 12 below for parameters and allowed time intervals).
- Blood sampling for translational medical investigations with **Analysis Kit** only in patient who have given informed consent – part 3.
- Tumor evaluation (see section 10.2.1 for examinations to be done and TABLE 12 below for allowed time intervals).
- Cardiac investigations (see TABLE 12 below examinations to be done and allowed time intervals).
- Quality of life assessment (see TABLE 12 below questionnaires and allowed time intervals).
- Pregnancy test (if applicable)

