10.2.2 Evaluation of Circulating Tumor Cells (CTC)

Count of CTC

For counting CTCs are isolated by means of the CellSearch® Circulating Tumor Cell Kit (Veridex LLC, Raritan, USA).

Assessment of HER2 Status of Circulating Tumor Cells

Blood samples will be collected into CellSave tubes (Veridex Inc.). The CellSearch Epithelial Cell Test (Veridex Inc.) will be applied for CTC enrichment and enumeration. The method has been described in detail elsewhere (Riethdorf et al. 2007). In brief, CTCs are captured from peripheral blood by anti-epithelial cell adhesion molecule (EpCAM)-antibody-bearing ferrofluid and subsequently identified by cytokeratin-positivity/negativity for the leukocyte common antigen CD45 and 4',6-diamidino-2-phenylindole (DAPI) staining to ensure the integrity of the nucleus. A blood sample is considered positive when at least one CTC is present based on the prognostically relevant cut-off as previously published (Cristofanilli et al. 2004, Budd et al. 2006). HER2 expression of CTCs will be characterized within the CellSearch assay by addition of a fluorescein isothiocyanate (FITC)-labeled anti-HER2 antibody (CellSearch tumor phenotyping reagent HER2, Veridex Inc.), as described previously (Hayes et al. 2002, Meng et al. 2004, Riethdorf et al. 2010). The intensity of the HER2-specific immunofluorescence will be categorized into negative (0), weak (1+), moderate (2+), and strong (3+). CTCs are considered HER2 negative, if all measured CTCs have a moderate HER2 staining (2+) or less based on the cut-off level published by Riethdorf et al. 2010.

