15.3 Sample Size Assumptions

In the DETECT IV trial, the primary objective is to estimate treatment efficacy in patients with HER2-negative metastatic breast cancer and persisting exclusively HER2-negative circulating tumor cells; treatment efficacy will be assessed by the CTC clearance rate in patients treated with everolimus/ribociclib combined with endocrine therapy (everolimus/ribociclib cohort) or by progression-free survival (PFS) in patients treated with eribulin (eribulin cohort). There is no statistical hypothesis underlying the primary analysis.

The following assumptions were made regarding the sample size of patients available for the DETECT IV trial:

- anticipated number of at least 2000 patients with HER2-negative metastatic breast cancer that are to be screened for CTCs in DETECT IV and the related DETECT III trial (which focuses on patients with HER2-negative primary tumor and HER2-positive circulating tumor cells)
- evidence of CTCs (≥ 1) in 65% of patients with metastatic breast cancer (conservative estimate based on Botteri et al. 2010, Fehm et al. 2010, Pierga et al. 2012)
- evidence of exclusively HER2-negative CTCs in 70% of CTC-positive patients (conservative estimate based

on experience from the related DETECT III trial)
Based on these assumptions, the screening will result in about 910 patients with HER2-negative metastatic breast cancer and exclusively HER2-negative CTCs.

Everolimus/ribociclib cohort:

Assuming that 70% of breast cancer patients have a hormone-receptor positive primary tumor and 75% of these patients have postmenopausal status, there will be about 480 postmenopausal patients with hormone-receptor positive, HER2-negative metastatic breast cancer and persisting exclusively HER2-negative CTCs. Based on experience from the related DETECT III trial, a considerable proportion of these patients is expected to fulfill not all of the inclusion criteria, to meet some of the exclusion criteria, or to have an indication for chemotherapy, thus prohibiting the inclusion in the everolimus/ribociclib cohort. We estimate that only about 180 of the 480 patients with hormone-receptor positive, HER2-negative metastatic breast cancer and persisting exclusively HER2-negative CTCs can indeed be included in the everolimus/ribociclib cohort of the DETECT IV trial.

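### DIVa CTC clearance scores a move from at least one cell to zero with no confirmatory sample or untreated control, so some clearances are chance zeros, concentrated in patients entering with 1-4 cells

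*Protocol*

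**What the plan says.** Section 10.1.1 counts as cleared a patient who was positive before treatment and is among those "that show no evidence of CTCs in the blood after treatment". Sections 1.2.1 and the synopsis say the same. Entry uses the same one-cell rule (5.1): "At least one CTC has been detected in 7.5 ml patient blood by means of the CellSearch® Circulating Tumor Cell Kit". Section 10.2.2 sets positivity per sample: "A blood sample is considered positive when at least one CTC is present based on the prognostically relevant cut-off as previously published". The Analysis Kit (Table 3 in 2.10.1) holds "Approx. 50 ml (10 ml for CTC detection, 40 ml for additional research", and no replicate count or confirmatory draw is required.

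Section 15.2 states that the primary analysis has no hypothesis and that the clearance rate is the measure of treatment efficacy in DIVa. Sections 8.2.1.2 and 8.3.1.2 call the study non-randomized. Section 15.3 assumes 54% clearance and 80 evaluable patients per drug, with the first 90 recruited receiving everolimus and the next 90 ribociclib. Section 2.7.2 says that primary and secondary endpoints will be compared between these two cohorts.

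Section 6.3 also provides a pre-treatment Analysis Kit draw at the Inclusion Visit, "only in patient who have given informed consent" to translational sampling (part 3).

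**The concern.** At one to four cells per sample, the count is close to the limit of what one tube can show. A patient whose true concentration is unchanged can give one cell in one tube and none in the next. Selecting on at least one cell and then scoring a later zero builds in some regression to zero. With no control arm, nothing in the design separates these zeros from a drug effect.

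Two things are at stake. The reported rate is read as efficacy although part of it would occur without any drug. That part also depends on how many patients enter with low counts, so two cohorts recruited one after the other can differ in clearance without any difference between the drugs.

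**Working it through.** **The plan's own figures.** For p = 0.54 and n = 80, the 95% interval width is 2 × 1.96 × √(0.54 × 0.46 / 80) = 21.8% (Wald), 23.1% with continuity correction, and 22.7% by Clopper-Pearson. The stated width of about 23% reproduces. So does 160 × 0.68 = 109 patients with at least five CTCs.

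**Inputs.** From 15.3: "evidence of CTCs (≥ 1) in 65% of patients with metastatic breast cancer", and 68% of CTC-positive patients with at least five, so P(≥5) = 0.65 × 0.68 = 0.442. From 2.3, as a range: "five or more CTCs are detected in about 40-50% of MBC patients".

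**Assumptions not in the protocol.** Counts are Poisson within a patient and true concentrations are gamma-distributed between patients. True levels do not change between samples. The second sample is a single one of equal volume.

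**Fit.** Solving for P(≥1) = 0.65 and P(≥5) = 0.442 gives shape r = 0.248 and mean 16.9 cells per 7.5 ml, so b = r/mean = 0.0147.

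**Zero in the second sample, no true change.**
- P0 = (b/(b+1))^r = 0.350 and P00 = (b/(b+2))^r = 0.295.
- Overall: (P0 − P00)/(1 − P0) = 0.055/0.650 = 8.4%.
- Entry count k: ((b+1)/(b+2))^(r+k), which gives 42.5% at one cell, 21% at two, 11% at three and 5% at four.
- Pooled: 26% for 1-4 cells and 0.3% for five or more. About 13% of positives enter with exactly one cell.

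**Sensitivity.**

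| Variant | Overall | At one CTC |
|---|---|---|
| Gamma-Poisson, 65% / 68% | 8.4% | 42.5% |
| Lognormal-Poisson, same inputs | 9.7% | 46% |
| 10-30% of patients truly without CTCs | 7.8% down to 4.2% | 40% down to 24% |
| P(≥1) 65-85%, P(≥5) 40-50% | about 6-12% | about 28-47% |
| Only exclusively HER2-negative patients enter (low counts enriched) | about 10-11%, at most 0.084/0.70 = 12% | not computed |

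**Share of an observed 54%.** Only patients who are not truly cleared can clear by chance. If a fraction q truly clears, independently of baseline count, then q + (1 − q) × 0.084 = 0.54. This gives q = 0.456/0.916 = 0.498. The chance part is 0.502 × 0.084 = 4.2 points, about 3 of 80 patients, or 4.2/23 = 18% of the interval width.

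**Cohort comparison, illustration.** Suppose 75% of one cohort and 62% of the other enter with at least five CTCs. Both values lie within the 62-77% implied by 2.3 (0.40/0.65 to 0.50/0.65). With no true clearance, chance zeros differ by 0.13 × (0.26 − 0.003) = 3.3 points. If half of each cohort truly clears regardless of count, the difference is about 0.50 × 3.3 = 1.7 points.

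**The case against.** The strongest case against is that the primary analysis only estimates a rate, no stated figure is wrong, and both drug groups share the same entry rule. Section 15.2 already plans exploratory work on CTC dynamics with various thresholds, and 15.3 plans a comparison based on five cells. A table by baseline count is ordinary analysis-plan content. This limits the point to interpretation. It does not remove it, because those plans concern secondary, exploratory objectives. They do not address the primary clearance rate or its comparison between cohorts, both of which the protocol itself fixes.

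Some stronger readings are tempting but not supported:
- **That 8 of the 54 points are noise.** The 8% applies to a population in which nobody truly clears. At 54% observed, the chance part is about half that. The 54% is itself an observed rate and may carry the same component, so nothing should be subtracted from it.
- **That 8% and 43% are facts.** The protocol gives no distribution of true counts between patients. Section 10.1.1 also fixes neither the volume nor the draw that counts as after treatment. If more than one negative draw were needed, chance clearance would be lower.
- **That the Inclusion Visit sample goes unused.** Section 2.10.2 makes it the baseline count in consenting patients, and 15.2 describes counts at all time points. It is just not set beside the primary rate.
- **That screening versus inclusion isolates sampling noise.** Section 6.1 allows the screening draw one week after prior anticancer therapy, so true levels may still be moving. Only consenting patients contribute.
- **That 10.2.2 misstates its sources.** Section 2.3 cites the same two studies for the prevalence of five or more cells, and 15.3 refers to published studies using a threshold of five. That is a tension in the text; whether it is an error cannot be judged without the sources.

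**Conclusion.** The point holds in limited form. Clearance as defined includes chance zeros: with no true change, about 8% overall (about 4-12%) and about 43% (24-47%) at one cell. These figures rest on Poisson sampling, an assumed distribution between patients, and a single second sample of equal volume. No variant tried gave zero.

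At 54% observed, the contribution is about 4 points if true clearance is unrelated to baseline count. It is smaller if true clearance concentrates in low counts, and larger if it concentrates in high ones. This is modest beside an interval 23 points wide, and that width stands. The clearer consequence is for the comparison in 2.7.2: chance clearance is about 26% at 1-4 cells and 0.3% at five or more, so a difference in baseline counts between the sequential cohorts biases it. The protocol gives no evidence that the counts will differ; it makes no provision if they do.

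**What to change.** Keep the endpoint and add to section 15.2:

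1. Report clearance by baseline count (1, 2-4, at least 5), with the stratum of at least five as a sensitivity analysis. Stratify or adjust the everolimus-ribociclib comparison for baseline count.
2. Among screening-positive patients who consented, report the proportion reading 0 at the Inclusion Visit Analysis Kit draw beside the primary rate. Label it a descriptive reference without study drug, and state the caveats of recent prior therapy and selection by consent.

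As a minor point, reconcile the description in 10.2.2 of one cell as the published prognostic cut-off with 2.3 and 15.3. No result depends on this.

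The cost is a little more analysis and a somewhat less favourable reading of the clearance rate. Both samples are already planned, so no new procedure is needed.

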10.1.2 Progression Free Survival (PFS)

PFS is defined as the time interval between the date of recruitment and the date of PD or death from any cause, whichever comes first.

10.1.3 Overall Survival

Overall survival is defined as the time interval between the date of recruitment and the date of death from any cause.

10.1.4 Overall Response Rate

The overall objective response rate applies only to patients with whom target lesions were defined at baseline. It is defined as the rate of CR and PR.

10.1.5 Clinical Benefit Rate

The clinical benefit rate applies to all patients. It is defined as the sum of the total number of patients with whom target lesions were defined and who achieve a complete or partial response and those patients who had stable disease for at least 6 months divided by the total number of patients in a treatment group.

10.1.6 New metastasis-free survival

New metastasis-free survival (nMFS), defined as time from recruitment to death or progression due to appearance of a new metastasis, whichever comes first.

10.1.7 Quality-adjusted survival

Quality-adjusted survival (as assessed by the Q-TWiST method), with the utility scores for the different health states being prospectively determined in the clinical trial subjects based on the EORTC QOL C30 questionnaire.

10.2 Evaluation of Endpoints

10.2.1 Tumor evaluation (Evaluation of response and progression of metastatic disease)

Examinations regarding tumor evaluation:

On each tumor evaluation (during pre-treatment period and regularly 3 month during randomized treatment period) the **same method** of assessment and **the same technique** should be used to characterize each identified and reported lesion at baseline and during follow-up. The following examinations have to be done:

- Clinical assessment of all lesions is mandatory. For tumor evaluation clinical lesions will only be considered measurable when they are superficial and ≥ 10 mm diameter. Documentation by color photography including a ruler is suggested.
- Imaging is performed as follows:
 - CT, MRI (Chest, Abdomen, Pelvis): CT is the preferred method of tumor evaluation. In certain circumstances MRI may be used instead, for details please refer to the RECIST-Guideline 1.1 (Eisenhauer 2009).

- CT, MRI (Head): A CT/MRI of the head is performed only if clinically indicated or if subject has a history of central nervous system metastases.
- Chest X-Ray: Chest X-Ray measurement of lesions is feasible, but not preferable. Lesions on chest x-ray are only acceptable as measurable lesions when they are clearly defined and surrounded by aerated lung. In case of performing CT-Scans there is no additional Chest X-Ray assessment necessary.
- Bone Scan and PET: Are not considered adequate imaging techniques to measure bone lesions. However, these techniques can be used to confirm the presence or disappearance of bone lesions (Eisenhauer 2009).
- Ultrasound: Ultrasound is not useful in assessment of lesion size and should not be used as a method of measurement. If new lesions are identified by ultrasound in the course of the study, confirmation by CT or MRI is advised (described in greater detail in Appendix II of the RECIST-guideline (Eisenhauer 2009). If there is concern about radiation exposure at CT, MRI may be used instead of CT in selected instances.
- PET/CT: Should not be substituted for dedicated diagnostic contrast enhanced CT scans for anatomically based RECIST measurements. However, if the CT performed as a part of a PET-CT is of identical diagnostic quality to a diagnostic CT (with i.v. and oral contrast) then the CT portion of the PET-CT can be used for RECIST measurements.
- Additional imaging is to be performed for assessment of further known lesions or if required by clinical suspicion of new lesions.
- Tumor markers are assessed on each tumor evaluation: CA15-3 is mandatory, CA125 and CEA are optional.
- Endoscopy, laparoscopy: These techniques must not be used for objective tumor evaluation. However biopsies obtained may be used to confirm complete response or assess relapse after complete response
- Cytology: The cytological confirmation of the neoplastic origin of any effusion that appears or worsens during treatment when the measurable tumor has met criteria for response or stable disease is mandatory to differentiate between response or stable disease (an effusion may be a side effect of the treatment) and progressive disease.

Definitions and guidelines regarding tumor evaluation

- At baseline during pretreatment period tumor lesions and/or lymph nodes are categorized measurable/non-measurable and target/non-target as follows:

Measurability:

A lesion is considered measurable if the longest diameter in the plane of measurement is at least

- 10 mm in case of CT scan
- 10 mm caliper measurement in case of clinical exam (lesions which cannot be accurately measured with calipers should be recorded as non-measurable)
- 20 mm in case of X-ray

Lymph nodes are considered pathologically enlarged and measurable if ≥ 15 mm in short axis when assessed by CT scan.

Any other lesions, including small lesions (longest diameter < 10 mm or pathological lymph nodes with ≥ 10 to < 15 mm short axis) as well as truly non-measurable lesion are considered non-measurable. Truly non-measurable lesions include: leptomeningeal disease, ascites, pleural and pericardial effusion, inflammatory breast disease, lymphangitic involvement of skin or lung, abdominal masses/abdominal organomegaly identified by physical exam that is not measurable by reproducible imaging techniques.

Target/non-target lesions:

If on baseline tumor evaluation there are at least two measurable lesions a maximum of five in total and a maximum of two per organ are selected as target lesions. In case of lymph nodes the length of the short axis, in case of other lesions the longest diameter is recorded. Target lesions should be selected on the base of their size (lesions with the longest diameter) and be representative of all involved organs, but in addition should be those which lend themselves to reproducible repeated measurements. The sum of the lesion diameters (LD) assessed for all target lesions is calculated and reported as baseline sum LD. All other lesions are considered non-target and reported without diameter whether measurable or not.

- On the regular tumor evaluations during treatment period, which are performed every 3 months LD is reassessed. All non-target lesions are reported “present”, “absent” or “unequivocal progression”.
- Generally:
Response and progression of metastatic disease is evaluated using the international guidelines Version 1.1 proposed by the RECIST committee (Eisenhauer 2009).
For detailed instruction on lesion measurements, follow-up of non-target lesions and special considerations regarding lymph nodes, bone lesions, cystic lesions, lesions not observed at baseline and lesions with prior

radiologic treatment please refer to the **RECIST guideline Version 1.1** (Eisenhauer 2009).

Assessment of tumor response

Tumor response is assessed as follows:

- *Evaluation of target lesions:*

Complete Response (CR):	Disappearance of all target lesions. Any pathological lymph nodes (whether target or non-target) must have reduction in short axis to < 10 mm
Partial Response (PR):	At least a 30% decrease in the sum of diameters of target lesions, taking as reference the baseline sum diameters
Progressive Disease (PD):	At least a 20% increase in the sum of diameters of target lesions, taking as reference the smallest sum on study (this includes the baseline sum if that is the smallest sum on study). In addition to the relative increase of 20% the sum must also demonstrate an absolute increase of at least 5 mm. (Note: The appearance of one or more lesions is also considered progression)
Stable Disease (SD):	Neither sufficient shrinkage to qualify for PR nor sufficient increase to qualify for PD, taking as reference the smallest sum diameters while on study.

- *Evaluation of non-target lesions:*

Complete Response (CR):	Disappearance of all non-target lesions and normalization of tumor marker level. All lymph nodes must be non-pathological in size (<10 mm short axis)
Non-CR/Non-PD:	Persistence of one or more non-target lesions above normal limits
Progressive Disease (PD):	Unequivocal progression of existing non-target lesions

- *Evaluation of Overall Response:*

From evaluations of target and non-target lesions and accounting for newly observed lesions Overall Response is assessed as described in the following tables:

Target Lesions	Non-Target Lesions	New Lesions	Overall Response
CR	CR	No	CR
CR	Non-CR/Non-PD	No	PR
CR	Not evaluated	No	PR
PR	Non-PD or not at all evaluated	No	PR
SD	Non-PD or not at all evaluated	No	SD
Not at all evaluated	Non-PD	No	Not evaluable
PD	Any	Yes or No	PD
Any	PD	Yes or No	PD
Any	Any	Yes	PD

Table 27: Evaluation of patients with target disease

Non-Measurable Lesions	New Lesions	Overall Response
CR	No	CR
Non-CR/non-PD	No	Non-CR/non-PD
Not at all evaluated	No	Not evaluable
Unequivocal PD	Yes or No	PD
Any	Yes	PD

Table 28: Evaluation of patients with non-target disease only

Data to be reported regarding tumor evaluations:

On each tumor evaluation the following data are reported (definitions see above):

- Concerning each lesion/lymph node:
 - Location
 - Measurable/non-measurable
 - Target/non-target
- Concerning non-target lesions: Present/absent/unequivocal progression
- Concerning target lesions only:
 - Lesion diameter (LD) (short axis in case of lymph nodes, longest axis in other cases according to RECIST guidelines)
 - Sum of lesion diameters (LD) assessed for all target lesions
- Tumor marker level

Beyond, the following information is provided on tumor evaluations during randomized treatment period:

- Response of target lesion (CR, PR, PD, SD)
- Response of non-target lesion (Present/absent/unequivocal progression: CR, Non-CR/Non-PD, PD)

At conclusion of the randomized treatment period the following information is provided:

- Overall Response

